1.2.4.3. Safety in SGNLVA-001

Safety Data of LV Monotherapy q3wk

As of 26 July 2021, LV monotherapy has been evaluated in 191 subjects with mBC with the majority of subjects receiving LV 2.0 mg/kg (n=36) and LV 2.5 mg/kg (n=141) q3wk. The most common treatment-emergent adverse events (TEAEs) occurring in $\geq 20\%$ of subjects with mBC treated with LV monotherapy using the q3wk schedule (n=191) are shown in [Table 1](#). This includes all patients who received LV monotherapy q3wk from 0.5 mg/kg to 2.8 mg/kg dose.

The most common Grade 3 or higher events were neutropenia (25.7%), anemia (9.9%), fatigue (8.9%), nausea (6.8%), abdominal pain, dehydration, and dyspnea (5.2% each). Serious adverse events (SAEs) were reported in 71 subjects (37.2%) with 36 subjects (18.8%) experiencing SAEs that were considered at least possibly related to LV. The most commonly reported SAEs included abdominal pain (3.7%), dehydration, nausea (3.1% each), neutropenia, vomiting (2.6% each), constipation, and febrile neutropenia (2.1% each) (Seagen Inc., data on file).

Table 1: Treatment-emergent adverse events occurring in ≥20% of subjects treated in Study SGNLVA-001 by preferred term – LV monotherapy q3wk

Preferred Term ^a , n (%)	Total (N=191)
Fatigue	112 (58.6)
Nausea	88 (46.1)
Constipation	78 (40.8)
Decreased appetite	72 (37.7)
Peripheral sensory neuropathy	69 (36.1)
Alopecia	68 (35.6)
Diarrhoea	59 (30.9)
Neutropenia	57 (29.8)
Abdominal pain	48 (25.1)
Arthralgia	47 (24.6)
Vomiting	41 (21.5)

^a MedDRA Version 24.0

Note: For each preferred term, subjects are included only once, even if they experienced multiple events in that preferred term

LV=ladiratuzumab vedotin; MedDRA=Medical Dictionary for Regulatory Activities; q3wk=Day 1 every 21-day cycle.

Source: Seagen Inc., data on file.

Safety Data of LV Monotherapy q1wk

As of 26 July 2021, 81 subjects have been dosed with LV q1wk in SGNLVA-001 (20 subjects with 1.0 mg/kg, 52 subjects with 1.25 mg/kg, and 9 subjects with 1.5 mg/kg). LV monotherapy q1wk doses of 1.0 mg/kg, 1.25 mg/kg, and 1.5 mg/kg were safely delivered without DLTs.

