The adverse event (AE) profile occurring in >20% subjects (Seagen Inc., data on file) in subjects dosed with LV monotherapy using the q1wk schedule is shown in Table 2. The most common Grade 3 or higher events for all subjects that received LV q1wk were neutropenia (21.0%), fatigue (14.8%), hyperglycemia, neutrophil count decrease (11.1% each), hypokalemia, hypophosphatemia (9.9% each), and nausea (8.6%). SAEs were reported in 35 subjects (43.2%). Of those, SAEs in 17 subjects (21.0%) were considered at least possibly related to LV. The most commonly reported SAEs included fatigue, febrile neutropenia, nausea (3.7% each), abdominal pain, dehydration, hyponatremia, and neutrophil count decrease (2.5% each) (Seagen Inc., data on file).

Table 2: Treatment-emergent adverse events occurring in ≥20% subjects treated in Study SGNLVA-001 – LV monotherapy q1wk

Preferred Term ^a , n (%)	1 mg/kg (N=20)	1.25 mg/kg (N=52)	1.5 mg/kg (N=9)	Total (N=81)
Fatigue	12 (60.0)	31 (59.6)	7 (77.8)	50 (61.7)
Nausea	10 (50.0)	31 (59.6)	4 (44.4)	45 (55.6)
Peripheral sensory neuropathy	3 (15.0)	28 (53.8)	5 (55.6)	36 (44.4)
Constipation	8 (40.0)	20 (38.5)	6 (66.7)	34 (42.0)
Decreased appetite	6 (30.0)	23 (44.2)	2 (22.2)	31 (38.3)
Diarrhoea	9 (45.0)	16 (30.8)	4 (44.4)	29 (35.8)
Vomiting	10 (50.0)	16 (30.8)	2 (22.2)	28 (34.6)
Myalgia	4 (20.0)	16 (30.8)	4 (44.4)	24 (29.6)
Neutropenia	4 (20.0)	14 (26.9)	6 (66.7)	24 (29.6)
Abdominal pain	5 (25.0)	17 (32.7)	1 (11.1)	23 (28.4)
Alopecia	5 (25.0)	14 (26.9)	3 (33.3)	22 (27.2)
Hypokalaemia	5 (25.0)	14 (26.9)	3 (33.3)	22 (27.2)
Arthralgia	4 (20.0)	16 (30.8)	1 (11.1)	21 (25.9)
Dyspnoea	4 (20.0)	13 (25.0)	4 (44.4)	21 (25.9)
Weight decreased	3 (15.0)	12 (23.1)	4 (44.4)	19 (23.5)
Muscular weakness	1 (5.0)	13 (25.0)	4 (44.4)	18 (22.2)
Dizziness	4 (20.0)	11 (21.2)	2 (22.2)	17 (21.0)
Insomnia	1 (5.0)	14 (26.9)	2 (22.2)	17 (21.0)

^a MedDRA Version 24.0

Note: For each preferred term, subjects are included only once, even if they experienced multiple events in that preferred term. The 20% cutoff is based on percentages in the “Total” column.

LV=ladiratuzumab vedotin; MedDRA=Medical Dictionary for Regulatory Activities; q1wk= Days 1, 8, and 15 every 21-day cycle.

Source: Seagen Inc., data on file

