7.6.1. Adverse Events

7.6.1.1. Definitions

Adverse Event

According to the International Council for Harmonisation (ICH) E2A guideline Definitions and Standards for Expedited Reporting, and 21 Code of Federal Regulations (CFR) 312.32, investigational new drug (IND) Safety Reporting, an AE is any untoward medical occurrence in a subject or clinical investigational subject administered a medicinal product and which does not necessarily have a causal relationship with this treatment.

The following information should be considered when determining whether or not to record a test result, medical condition, or other incident on the Adverse Events and Pre-existing Conditions CRF:

- From the time of informed consent through the day prior to study Day 1, only study protocol-related AEs should be recorded. A protocol-related AE is defined as an untoward medical event occurring as a result of a protocol mandated procedure.
- All medical conditions present or ongoing predose on study Day 1 should be recorded.
- All AEs (regardless of relationship to study drug) should be recorded from study Day 1 (during and post-dose) through the end of the safety reporting period (see Section 7.6.1.3). Complications that occur in association with any procedure (eg, biopsy) should be recorded as AEs whether or not the procedure was protocol mandated.
- Changes in medical conditions and AEs, including changes in severity, frequency, or character, during the safety reporting period should be recorded.

In general, an abnormal laboratory value should not be recorded as an AE unless it is associated with clinical signs or symptoms, requires an intervention, results in a SAE, or results in study termination or interruption/discontinuation of study treatment. When recording an AE resulting from a laboratory abnormality, the resulting medical condition rather than the abnormality itself should be recorded (eg, record "anemia" rather than "low hemoglobin").

Serious Adverse Events

An AE should be classified as an SAE if it meets one of the following criteria:

Fatal:	AE resulted in death
Life threatening:	The AEs placed the subject at immediate risk of death. This classification does not apply to an AE that hypothetically might cause death if it were more severe.

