7.6.3. Clinical Laboratory Tests

The following safety laboratory assessments will be performed by local laboratories at the designated time points (see [Appendix A](#), [Appendix B](#), [Appendix C](#), and [Appendix D](#)) during the course of the study. Results of all clinical laboratory tests except pregnancy and PSA tests are to be submitted to iRIS. Instructions for submission to iRIS are located in the iRIS Manual.

- Serum chemistry panel: including sodium, potassium, blood urea nitrogen/blood urea, creatinine, calcium, albumin, and magnesium.
- Liver function tests including total bilirubin, alkaline phosphatase, ALT, and AST
- CBC with differential: white blood count, hemoglobin, hematocrit and platelets; and the differential including, but not limited to, neutrophils, lymphocytes, and monocytes
- PSA test (prostate cancer patients only)
- Testosterone measurement (at Screening, prostate cancer patients only)
- Blood glucose
 - Fasting blood glucose is only required at screening. If fasting blood glucose is elevated, a repeat assessment must be obtained.
- HbA1c: if HbA1c is elevated during screening, HbA1c assessment must be repeated to confirm
- The estimated GFR should be calculated using the MDRD equation as applicable, with serum creatinine (Scr) reported in mg/dL.

$$\text{GFR (mL/min/1.73 m}^2\text{)} = 175 \times (\text{Scr})^{-1.154} \times (\text{Age})^{-0.203} \times (0.742 \text{ if female}) \times (1.212 \text{ if African American})$$

- Thyroid function tests, including TSH, T3 or free T3, and free T4 (Part C Arm 2 and Arm 3).

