9.3.8.4. Clinical Laboratory Results

Summary statistics of laboratory results and changes from baseline will be tabulated by scheduled visit. Grading of laboratory values will be assigned programmatically per the NCI CTCAE v5.0. Shift tables comparing the worst post-baseline to baseline CTCAE grade will be presented. Laboratory values will be listed with grade per CTCAE and flagged when values are outside the normal reference range.

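### Section 7.6.3 does not require serum phosphate, although the protocol's background reports Grade 3 or higher hypophosphatemia in 9.9% of weekly-dosed subjects, so silent falls would be measured only where a site chooses to

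*Protocol*

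**What the plan says.** Protocol Section 7.6.3 defines the panel: "Serum chemistry panel: including sodium, potassium, blood urea nitrogen/blood urea, creatinine, calcium, albumin, and magnesium". The neighbouring liver entry reads "Liver function tests including total bilirubin, alkaline phosphatase, ALT, and AST"; alkaline phosphatase is an enzyme and says nothing about serum phosphate. Phosphate is absent from the visit lists in Sections 6.2 to 6.4, from Appendices A to D, and from SAP Section 6.6.2. Testing is decentralised: "The following safety laboratory assessments will be performed by local laboratories at the designated time points".

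Protocol Section 1.2.4.3 gives the background for weekly dosing: "As of 26 July 2021, 81 subjects have been dosed with LV q1wk in SGNLVA-001". Its list of the commonest Grade 3 or higher events for all weekly-dosed subjects includes "hypokalemia, hypophosphatemia (9.9% each), and nausea (8.6"%).

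Two further rules decide where an abnormal value is recorded. Section 7.6.1.1 says "In general, an abnormal laboratory value should not be recorded as an AE unless it is associated with clinical signs or symptoms", and then allows recording if the abnormality needs an intervention, amounts to an SAE, or interrupts or ends study treatment or participation. Section 9.3.8.4 plans summary statistics and changes from baseline at scheduled visits, with programmatic CTCAE grading, and says "Shift tables comparing the worst post-baseline to baseline CTCAE grade will be presented".

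**The concern.** The protocol reports two electrolyte toxicities at the same Grade 3 or higher rate. It requires the analyte for one and not for the other, and gives no reason for the difference.

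The consequence is uneven ascertainment. Section 7.6.1.1 generally keeps silent laboratory abnormalities out of the AE data, so the laboratory data are the main record of them. Those data can summarise only what was measured. With local laboratories and an unlisted analyte, measurement depends on site habit.

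Safety and tolerability is a secondary objective (Section 2), and Section 9.1 justifies the sample size partly by how well it characterises common AEs. Weekly LV is given to up to 252 subjects in Part B and to 30 in Part C Arm 3. A low hypophosphatemia rate in those groups could reflect few events or little testing, and the data would not separate the two. The primary endpoint is not affected.

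**Working it through.** **Inputs**
- Grade 3 or higher hypophosphatemia with weekly LV: 9.9% (Section 1.2.4.3).
- Denominator: 81, made up of 20 at 1.0 mg/kg, 52 at 1.25 mg/kg and 9 at 1.5 mg/kg (Section 1.2.4.3).
- Cohort or arm size: 30; Part B maximum: 252 (Section 9.1).

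**Step 1. Reproduce the protocol's rate.** 8/81 = 9.88%, which rounds to 9.9%. The neighbouring counts do not fit: 7/81 = 8.64% and 9/81 = 11.11%. The rate is therefore 8 subjects.

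**Step 2. Reproduce the protocol's detection table (Section 9.1, N = 30).** P(at least one) = 1 − (1 − p)^30.
- p = 5%: 1 − 0.95^30 = 78.5% (stated 79%).
- p = 10%: 1 − 0.90^30 = 95.8% (stated 96%).

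Both reproduce. The formula treats every event as observed; for a laboratory toxicity, that presumes the analyte is measured.

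**Step 3. Precision of the background rate.** The exact (Clopper-Pearson) 95% CI for 8/81 is 4.4% to 18.5%.

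**Step 4. Carry the rate over (assumption).**

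| Quantity | At 8/81 | Over the 95% CI |
|---|---|---|
| Expected cases in 30 | 30 × 8/81 = 2.96 | 30 × 0.0436 = 1.3 to 30 × 0.1854 = 5.6 |
| Chance of at least one in 30 | 1 − (73/81)^30 = 95.6% | 74% to 99.8% |
| Expected cases in 252 (full Part B) | 252 × 8/81 = 24.9 | 11 to 47 |

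**Step 5. Trace a Grade 3 or higher fall through the plan.**

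| Type of case | Recorded as an AE (7.6.1.1)? | In the laboratory data (9.3.8.4)? |
|---|---|---|
| Symptomatic, treated, serious, or interrupting treatment | Yes, once identified | Only if the site tested phosphate |
| Silent and untreated, site tests phosphate | Generally no | Possible |
| Silent and untreated, site does not test | No | No |

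Only the last row is lost entirely. The documents do not allow its share of the 2.96 expected cases to be estimated.

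**The case against.** Several points on the other side are sound.

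- **Capture is not nil.** A reader might infer that no case would be found by the laboratory, or that the toxicity disappears from both the AE and the laboratory tables. The documents support neither. The panel is introduced by a non-exclusive word, so a local laboratory may report phosphate, and symptomatic or treated cases remain AEs. The openness has limits: the blood count item in the same list is worded "the differential including, but not limited to, neutrophils, lymphocytes, and monocytes", and the chemistry item has no such phrase. Permission to test is also not a requirement to test.
- **The 9.9% is an AE rate.** The documents do not say whether SGNLVA-001 measured phosphate routinely. If its cases came from clinically prompted testing, the same route exists here and understatement relative to that study need not follow. If they came from a routine panel, the concern is stronger.
- **Carry-over is uncertain.** The 81 subjects had breast cancer, and 9 received 1.5 mg/kg weekly, a weekly dose not used in this study. No rate by dose is given. For Part C Arm 3, the Grade 3 or higher events listed in Section 1.3.3.2 for LV plus pembrolizumab do not include hypophosphatemia, but that list pools 91 every-3-week with 45 weekly subjects.
- **The signal is for weekly dosing.** Hypophosphatemia is not among the common Grade 3 or higher events listed for every-3-week LV.
- **Shift tables are not assured.** The Section 5.6 note says CTCAE version 5 grades hyperglycemia by its management and not by the glucose value, so a measured value does not always yield a grade. SAP Section 6.6.2 makes shift tables optional.
- **No passage contradicts another,** and the iRIS Manual, which might list reported analytes, is not available.

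These points narrow the claim and the remedy. None explains why one of two equally frequent electrolyte toxicities has its analyte required and the other does not. The q1wk dose-modification table (Table 12, footnote b) also makes uninterrupted treatment with a Grade 3 or 4 electrolyte abnormality conditional on a management plan and regular monitoring, which presupposes detection.

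**Conclusion.** The point holds in a limited form. Phosphate is not required, although the protocol's own background puts Grade 3 or higher hypophosphatemia at 8 of 81 weekly-dosed subjects (9.9%, 95% CI 4.4% to 18.5%), level with hypokalemia. The gap is in systematic, uniform measurement: silent falls are measured at the site's choice, so the rate may be understated and may differ between sites for reasons unrelated to the drug. It is not a total loss of capture.

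If the rate transfers, about 3 of 30 subjects per weekly cohort or arm would be affected, with a 95.6% chance of at least one case (74% to 99.8%). That rests on breast cancer data applying to these tumors and, for Arm 3, to the combination. How many of those cases would go unmeasured cannot be derived from the documents.

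This should be changed. It affects a secondary safety objective and leaves the primary analysis untouched.

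**What to change.** Add serum phosphate to the chemistry panel in Section 7.6.3 at the chemistry time points already scheduled, at least for weekly dosing: Part B and Part C Arm 3 (Appendices A, C and D). Extending it to the other schedules would be for uniformity, since the cited signal is for weekly dosing. Report phosphate in the Section 9.3.8.4 summaries and changes from baseline by visit, and include it in shift tables only if the CTCAE v5.0 grade can be derived from the measured value. If the omission is deliberate, state the reason in Section 7.6.3.

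Subjects past baseline when the change takes effect will have no required baseline value, so the report should state from which protocol version phosphate was required.

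The cost is one extra local analyte per existing chemistry sample and one more result to submit, with no added visit or blood draw. The change is to measurement and reporting only; no dosing or treatment rule is proposed.

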7.6.4. Physical Examination

Physical examinations should include assessments of the following body parts/systems: abdomen, extremities, head, heart, lungs, neck, and neurological. For adult subjects only, measurements of height obtained within the prior 12 months may be utilized.

7.6.5. Pregnancy Testing

For subjects of childbearing potential, a serum or urine β -hCG pregnancy test with sensitivity of at least 25 mIU/mL will be performed at baseline, within 3 days prior to Day 1 of each treatment cycle, at the EOT visit, and 24 weeks after EOT. A negative pregnancy result is required before the subject may receive LV on Day 1 of each 21-day cycle. Pregnancy tests may also be repeated as requested per institutional review board (IRB)/independent ethics committee (IEC) or if required by local regulations.

7.7. Appropriateness of Measurements

The safety measures that will be used in this trial are considered standard procedures for evaluating the potential adverse effects of study medications.

Response will be assessed according to RECIST v1.1 ([Appendix H](#)) ([Eisenhauer 2009](#)), which are standardized criteria for evaluating response in solid tumors. The intervals of evaluation in this protocol are considered appropriate for disease management.

Immunogenicity is commonly assessed for biologics; therefore, standard tests will be performed to detect the possible presence of specific antibodies to LV. PK assessments are also common in clinical studies to help characterize dose-exposure-response relationships.

8. DATA QUALITY CONTROL AND QUALITY ASSURANCE

8.1. Site Training and Monitoring Procedures

A study manual with instructions for study compliance and CRF completion will be provided. Prior to the enrollment of subjects at the site, Seagen Inc. or its designated clinical and medical personnel will review the following items with the investigator and clinic staff:

- The protocol, study objectives, eligibility requirements, study procedures, registration and withdrawal processes
- Current IB /package insert
- Recording and reporting AEs and SAEs
- Enrollment goals and study timelines
- The CRF completion process and source documentation requirements
- Monitoring requirements
- IRB/IEC review and approval process
- Informed consent process
- Good clinical practice guidelines and related regulatory documentation requirements
- Key study team roles and responsibilities
- Investigational product storage, accountability, labeling, dispensing and record keeping
- Subject coding and randomization (if applicable)
- Study samples/specimen collection, handling and shipping
- Protocol compliance
- Clinical study record keeping, document retention, and administrative requirements

Monitoring visits will occur periodically, with frequency dependent on the rate of enrollment and workload at each site. During monitoring visits, the Seagen Inc. representative or designee will typically review regulatory documentation, CRFs, source documentation, and investigational product storage, preparation, and accountability. The CRFs will be reviewed for completeness, adherence to the provided guidelines, and accuracy compared to the source documents. The investigators must ensure that the monitor is allowed to inspect all source documents pertinent to study subjects, and must cooperate with the monitor to ensure that any problems noted in the course of the trial are resolved. The investigator must maintain a comprehensive and centralized filing system of all study-related documentation that is suitable for inspection by Seagen Inc. or its designated monitors and by quality assurance auditors, or representatives of regulatory authorities.

8.2. Data Management Procedures

Seagen Inc. will provide CRF Completion Guidelines for electronic CRF (eCRF) data entry. Study specific data management procedures will be maintained in the data management plan.

Queries resulting from edit checks and/or data verification procedures will be posted electronically in the eCRF.

8.3. Access to Source Data

The investigator will permit the sponsor's representatives to monitor the study as frequently as the sponsor deems necessary to determine that protocol adherence and data recording are satisfactory. Appropriate measures to protect subject confidentiality are to be employed during monitoring. The CRFs and related source documents will typically be reviewed in detail by the monitor at each site visit. Original source documents or certified copies are needed for review. This review includes inspection of data acquired as a requirement for participation in this study and other medical records as required to confirm that the information contained in the CRFs, such as disease assessments, AEs, and concomitant medications, is complete and correct. Other study records, such as correspondence with the sponsor and the IRB/IEC and screening and drug accountability logs will also be inspected. All source data and study records must also be available for inspection by representatives of regulatory authorities and the IRB/IEC.

8.4. Accuracy and Reliability of Data

Steps to be taken to assure the accuracy and reliability of data include:

- The selection of qualified investigators and appropriate study centers.
- Review of protocol procedures with the investigators and associated personnel prior to the study.
- Periodic monitoring visits by the designated monitor(s).
- CRFs will be reviewed for accuracy and completeness during monitoring visits to the study centers and/or by centralized monitoring. Any discrepancies will be resolved with the investigator or designees as appropriate.

8.5. Quality Assurance Procedures

The Research and Development Quality group or its designee may conduct audits at the clinical site or other study-related facilities and organizations. Audit reports will be retained by the Research and Development Quality group of Seagen Inc. as part of the written record.

8.6. Data Handling and Record Keeping

8.6.1. Data Handling

It is the investigator's responsibility to ensure the accuracy, completeness, legibility, and timeliness of the data reported to the sponsor in the CRFs and in all required reports. Data reported on the CRF that is derived from source documents should be consistent with the source documents or the discrepancies should be explained.

Any change or correction to a CRF will be maintained in an audit trail within the electronic data capture system. Data changes may only be made by those individuals so authorized. The investigator should retain records of the changes and corrections, written and/or electronic.

8.6.2. Investigator Record Retention

The investigator shall retain study drug disposition records and all source documentation (such as original laboratory reports, inpatient or office patient records) for the maximum period required by the country and institution in which the study will be conducted, or for the period specified by Seagen Inc., whichever is longer. The investigator must contact Seagen Inc. prior to destroying any records associated with the study. If the investigator withdraws from the study (due to relocation, retirement, etc.), the records shall be transferred to a mutually agreed upon designee, such as another investigator or IRB/IEC. Notice of such transfer will be provided in writing to Seagen Inc.

